### 4.2 Description of Trial Procedure

Patients will be treated with 2 priming doses of MVA-BN-Brachyury (Doses 1 and 2) and 1 dose of FPV-Brachyury (Dose 3) prior to initiation of radiotherapy. MVA-BN-Brachyury will be administered on Day 0 and approximately Day 14 (+ / - 2 days) followed by FPV-Brachyury on approximately Day 28 (+ / - 2 days). Radiotherapy will begin at least 2 weeks and not more than 4 weeks after first administration of FPV-Brachyury (Dose 3). Radiotherapy will proceed according to the dose and schedule selected by the treating radiation oncologist with guidelines detailed in [Section 6.3.1.2](#). The trial team must collect documentation of the dose and schedule of radiotherapy administered. The dose and schedule must comply with radiotherapy minimum requirements as defined in [Section 6.3.1](#).

At least 2 weeks following completion of radiotherapy (or upon resolution of any reversible AEs related to radiotherapy to Grade 1 or baseline if ongoing beyond 2 weeks), the patient will resume vaccination with FPV-Brachyury (Dose 4) and proceed to ongoing booster doses with FPV-Brachyury at 4-week intervals until 4 booster doses with FPV-Brachyury have been administered (Doses 4, 5, 6, 7). Subsequent vaccine doses will be administered in 12-week intervals through

approximately 2 years beyond completion of radiotherapy (Doses 8, 9, 10, 11, 12, 13). A final visit will occur 30 days after the last treatment visit.

**Figure 7 Trial Vaccine Schedule**

#### 4.2.1 Screening Phase

The screening evaluation will be conducted within 16 days before initiating treatment unless otherwise specified:

##### 4.2.1.1 Clinical Evaluation

- History and physical examination including vital signs (blood pressure, pulse, oxygen saturation, and temperature) Special attention should be paid to any history of vaccine allergies.
- Height and weight
- ECOG Performance status determination

##### 4.2.1.2 Laboratory Studies

To be performed at any time before Screening/ Baseline:

- Confirmation of diagnosis by Site Pathology Department.

To be performed within 6 months prior to Screening/ Baseline:

- Screening for HIV
- Screening for Hepatitis B and C.

To be performed within 16 days prior to Screening/ Baseline:

- Complete blood count plus differential and platelet count
- Serum chemistries (Na+, K+, Cl, CO2, glucose, BUN, creatinine, albumin, calcium, alkaline phosphatase, ALT, AST, total bilirubin, TSH)
- Antinuclear antibody titer (ANA)
- Beta-HCG for females of childbearing potential (repeated Beta-HCG [serum or urine] tests within 48 hours prior to treatment). Females of childbearing potential: A female of childbearing potential is a woman who:
  - Has started menses
  - Has not undergone a hysterectomy or bilateral oophorectomy
  - Has not been naturally postmenopausal for at least 24 consecutive months (i.e. has had menses at any time in the preceding 24 consecutive months)
  - Women of childbearing potential and sexually active males must be strongly advised to use an accepted and effective method of contraception or to abstain from sexual intercourse for the duration of their participation in the trial
- CD4:CD8 ratio, CD3, 4, 8, 19 subsets and Natural Killer (NK) markers (baseline, about day 28 and around day 85 prior to vaccination)

**4.2.1.3 Electrocardiogram (ECG)**

Within 28 days prior to protocol enrollment.

**4.2.1.4 Scans and X-Rays**To be performed within 28 days prior to the protocol enrollment:

- Computed Tomography (CT) of the chest/abdomen/pelvis
- Magnetic resonance imaging (MRI) of target lesions if present in: sacrum, spine, or clivus
  - MRI should include a T2 weighted fat-suppressed technique and/or fluid-attenuated inversion recovery or short TI Inversion Recovery to ensure differentiation from surrounding tissue

## 4.2.2 Active Trial Phase

Medical assessment and ECOG performance status will be completed within 3 days prior to each vaccination. Medical assessments will include a complete neurologic examination including documentation of cranial nerve, motor, sensory, cerebellar, and deep tendon reflex examinations.

### 4.2.2.1 Laboratory Assessments

- Complete Blood Count (CBC)/differential, with platelet count.
- Serum chemistries (Na+, K+, Cl, CO2, glucose, BUN, creatinine, albumin, calcium, alkaline phosphatase, ALT, AST, total bilirubin)
- Antinuclear antibody titer (if autoimmune toxicity is observed)
- CD4:CD8 ratio, CD3, 4, 8, 19 subsets and NK markers (to be drawn only on same day as blood for correlative biomarker studies research labs; see [Section 7](#))

These laboratory tests will be drawn prior to each vaccination for all patients unless otherwise indicated. For FOCBP, a serum or urine Beta-HCG test will be drawn within 48 hours prior to each vaccination. At a minimum, CBC, serum creatinine, and electrolytes will be obtained prior to each vaccination. Laboratory studies will be repeated more frequently if clinically indicated, and any abnormalities potentially related to treatment will be followed until they have resolved, or have been determined to not be treatment-related.

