Medical assessments include a complete neurologic examination including documentation of cranial nerve, motor, sensory, cerebellar, and deep tendon reflex examinations; interim history (since last visit); vital signs; physical examination (at baseline); targeted physical exam (Day 0-28, End of Radiation +2-+110 weeks, and Post-treatment follow up visits) and ECOG performance status. To be performed within 3 days prior of each dose of vaccine. Repeat medical assessment is not required at baseline if history and physical has been performed within 3 days of vaccine administration on day 0.

Serum HIV antibody should be completed within 6 months of initiating treatment.

Serum hepatitis B & C antibody should be completed within 6 months of initiating treatment.

Chemistry panel: Na+, K+, Cl, CO2, glucose, (BUN), creatinine, albumin, alkaline phosphatase, ALT, AST, total bilirubin, thyroid stimulating hormone (TSH), calcium, and ANA to be performed within 16 days prior to screening/ baseline per protocol. TSH is optional after screening visit.

In females of child-bearing potential, Beta-HCG to be done at baseline 48 hours prior to treatment and within 48 hours of any dose of vaccine or radiation.

CT chest, abdomen, and pelvis and MRI (if target lesion is best visualized by MRI)

Correlative biomarker studies (blood): 6 (10 mL) green top sodium heparin tubes for PBMC; 1 (8.5 mL) SST tubes for serum samples.

Radiotherapy schedule and dose selected by treating radiation oncologist. Radiotherapy will begin at least 2 weeks and ideally not more than 4 weeks after first administration of FPV-Brachyury (Dose 3).

 RECIST based assessment includes using RECIST principles (see [Section 10.5](#)) to measure the “target” lesions, defined as those meeting RECIST requirements for measurability and those that will be treated with radiation as defined by minimum requirements of the protocol. “Non-target” lesions may include those that are not measurable by RECIST or those that are measurable and not treated with radiotherapy at the dose required by protocol (per [Section 6.3.1](#)).

Time noted is from end of radiation or until resolution of AEs related to radiation, whichever is later

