### FPV-Brachyury

- FPV-Brachyury is a liquid-frozen, highly attenuated, live recombinant virus. It is administered as subcutaneous application.
- One FPV-Brachyury vial has a nominal virus titer of  $1 \times 10^9$  Inf.U in 0.5 mL of the drug product. The specific dose will be determined upon release testing of the drug product.
- For further details on the FPV-Brachyury vaccine, see current version of the Brachyury Investigator's Brochure.

No dose modifications will be allowed on this trial. Any patient who experiences a dose limiting toxicity or allergic or autoimmune toxicity as defined in [Section 4.2.5](#) will not receive any additional vaccinations.

[figure not shown]
If a scheduled dose of the vaccine is missed, the vaccine may be given within the treatment window specified in [Section 1.5](#). If the patient has a delay in vaccination not due to toxicity, the vaccine may be delayed for up to 42 days without removal of the patient from trial.

**Dosing Delay:** Patients should have resolution to  $\leq$  Grade 1 or return to baseline of all toxicities prior to the start of the next injection of the vaccine. If  $>$  Grade 2 toxicity attributed to vaccine persists for  $>$  28 days, the patient will not receive further vaccine injections and will be removed from vaccine therapy.

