**BRACHY-CHOR-001** 

Overall Treatment Period: All data collected from the first vaccination of trial treatment through the last trial visit (regardless of completion status) will be considered part of the overall treatment period. A final visit is planned for approximately 30 days after the last treatment visit. Specifically, the overall treatment period will consist of the pre-radiation vaccination period, radiation therapy period, post-radiation vaccination period 1 and post-radiation vaccination period 2, which are defined below.

**Pre-Radiation Vaccination Period**: The time from the date of first vaccination of MVA-BN-Brachyury to the day prior to the start of radiation therapy. Subjects should have received 2 doses of MVA-BN-Brachyury and 1 dose of fowlpox (FPV)-Brachyury during this period.

**BN-Brachyury:** Term that refers to both MVA-BN-Brachyury and FPV-Brachyury trial vaccines when used together in a prime-boost regimen.

**Radiation Therapy Period**: from the start date of radiation therapy to the day prior to resuming FPV-Brachyury injections.

**Post-Radiation Vaccination Period 1**: The time from the date of restart of FPV-Brachyury injections after radiation therapy to the day prior to the scheduled FPV-Brachyury injection at the End Radiation + 26 weeks visit. FPV-Brachyury will be administered every 4 weeks during this period.

**Post-Radiation Vaccination Period 2**: The time from the date of the FPV-Brachyury injection at the End Radiation + 26 weeks visit to the last scheduled trial visit (i.e., last injection of FPV-Brachyury + approximately 30 days). FPV-Brachyury will be administered every 12 weeks during this period.

**Treatment Emergent Adverse Events**: An AE with an onset on or after initiation of trial treatment, or an AE present at initiation of trial treatment that worsens (*i.e.*, increase in severity: On-Trial Grade > Baseline Grade) as determined by the investigator will be considered a treatment-emergent adverse event (TEAE). TEAEs are collected through the last scheduled visit (approximately 30 days after the last dose of trial product).

Serious Adverse Events (SAEs) and AEs of Special Interest (AESIs): SAEs and AESIs that occur on or after initiation of trial treatment through 30 days after the last dose of trial product are considered as TEAEs. SAEs and AESIs will be followed until resolution.

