## 3.5.8.3 Laboratory Data

Laboratory toxicities will be defined based on local lab normal ranges and NCI-CTCAE, Version 4.03 or higher. The number and percentage of subjects will be summarized by grade, using the most severe grade over the treatment periods (Pre-Radiation Vaccination Period, Radiation Therapy Period, Post-Radiation Vaccination Period 1 and Post-Radiation Vaccination Period 2). For lab parameters with both higher than normal and lower than normal severity grades, each finding will be treated as a different lab parameter. Shift from baseline to worst grade will also be summarized by treatment periods. For labs not covered by NCI-CTCAE, data will be summarized by High or Low based on normal lab ranges.

In addition, laboratory values will be listed, with out of range and NCI-CTCAE Grade 3/4 values flagged. For women of child-bearing potential, pregnancy test results will be presented in a listing.

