Serum hepatitis B & C antibody should be completed within 6 months of initiating treatment.

Chemistry panel: Na+, K+, Cl-, CO2, glucose, Blood Urea Nitrogen (BUN), creatinine, albumin, alkaline phosphatase, ALT, AST, total bilirubin, thyroid stimulating hormone, calcium, and ANA to be performed within 16 days prior to screening/ baseline per protocol. TSH is optional after screening visit.

In females of child-bearing potential, Beta-HCG to be done at baseline 48 hours prior to treatment and within 48 hours of any dose of vaccine or radiation.

CT chest, abdomen, and pelvis and MRI (if target lesion is best visualized by MRI)

Correlative biomarker studies (blood): 6 (10 mL) green top sodium heparin tubes for PBMC; 1 (8.5 mL) SST tubes for serum samples.

Radiotherapy schedule and dose selected by treating radiation oncologist. Radiotherapy will begin at least 2 weeks and ideally not more than 4 weeks after first administration of FPV-Brachyury (Dose 3).

10 RECIST based assessment includes using RECIST principles (refer to trial protocol Section 10.5 for the description of RECIST principles for the trial) to measure the "target" lesions, defined as those meeting RECIST requirements for measurability and those that will be treated with radiation as defined by minimum requirements of the protocol. "Non-target" lesions may include those that are not measurable by RECIST or those that are measurable and not treated with radiotherapy at the dose required by protocol

Time noted is from end of radiation or until resolution of AEs related to radiation, whichever is later

Vaccine doses will be administered in 12-week intervals through approximately 2 years of post-radiation treatment.

02 November, 2021

BRACHY-CHOR-001

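### The visit schedule omits chemistry at Dose 4 (End Radiation + 2 weeks), although Protocol 4.2.2.1 requires creatinine and electrolytes before every vaccination

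*Protocol*

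**What the plan says.** Protocol 4.2.2.1 lists the active-phase laboratory tests and then gives two rules. The general rule covers the whole list and ends with an exception clause: "These laboratory tests will be drawn prior to each vaccination for all patients unless otherwise indicated". The second sets a floor and has no exception clause: "At a minimum, CBC, serum creatinine, and electrolytes will be obtained prior to each vaccination".

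The schedule in Protocol 1.5, repeated in SAP Appendix 1, marks FPV-Brachyury and CBC at End Radiation + 2 weeks and leaves Chemistry blank. Footnote 5 defines that row; in the SAP copy it begins "Chemistry panel: Na+, K+, Cl-, CO2, glucose, Blood Urea Nitrogen (BUN), creatinine, albumin, alkaline phosphatase, ALT, AST, total bilirubin". No other row contains creatinine or electrolytes.

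Dose 4 is conditional on toxicity. Protocol 4.2 has vaccination resume at least 2 weeks after radiotherapy, or "upon resolution of any reversible AEs related to radiotherapy to Grade 1 or baseline if ongoing beyond 2 weeks". Schedule footnote 11 starts the visit clock accordingly: "Time noted is from end of radiation or until resolution of AEs related to radiation, whichever is later". The Dosing Delay paragraph of Protocol Section 6 asks for resolution to Grade 1 or lower, or "return to baseline of all toxicities prior to the start of the next injection of the vaccine".

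On reporting, SAP 3.5.8.3 summarizes laboratory toxicity by grade "using the most severe grade over the treatment periods (Pre-Radiation Vaccination Period, Radiation Therapy Period" and the two post-radiation periods). The SAP's General Definitions run the Radiation Therapy Period "from the start date of radiation therapy to the day prior to resuming FPV-Brachyury injections".

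**The concern.** The schedule is the table that sites work from. Followed as drawn, it produces blood counts but no creatinine or electrolytes before Dose 4, which the text does not permit. Dose 4 is also the visit where the omission is hardest to excuse. It is the first vaccination after radiation, it is held until radiation toxicity has settled, and the most recent scheduled chemistry predates radiation. Protocol Table 8 sets a dose constraint for the kidneys, so renal function after radiation is a reasonable thing to check.

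At stake are one safety check per patient and the completeness of the chemistry data around radiation. Confirming the safety of vaccine plus radiation is a secondary objective, and laboratory values are a named safety endpoint.

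**Working it through.** The plan states no figure on this point, so the check sets the schedule rows side by side and then works out the sampling gaps.

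**Visit by visit** (Protocol 1.5; SAP Appendix 1 shows the same pattern)

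| Vaccination visit | CBC | Chemistry |
|---|---|---|
| Day 0 | blank | blank |
| Day 14 | X | X |
| Day 28 | X | X |
| End Radiation + 2 weeks (Dose 4) | X | blank |
| End Radiation + 6, 10, 14, 26 weeks | X | X |
| End Radiation + 38, 50, 62, 74, 86, 98, 110 weeks | X | X |

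Visits after Day 0: 2 + 1 + 4 + 7 = 14. CBC is marked at 14 and Chemistry at 14 − 1 = 13. Day 0 is not a gap, because footnote 1 asks for laboratory studies within 16 days before treatment starts. The count follows the schedule. Protocol 4.2 numbers doses only to 13, which would make 12 visits after Day 0, still with one gap.

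A misaligned row is not the explanation: the Chemistry row has 12 cells for 12 visit columns, neighbouring rows line up, and both copies agree.

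**Scheduled gaps.** Inputs are the visit times and windows in Protocol 1.5. Gaps measured from Day 28 assume that radiation ends between Day 42 and Day 70, the schedule's approximate radiotherapy column, and that no unresolved adverse event moves the clock.

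- Age of the Day 28 chemistry at Dose 4: 42 + 14 − 28 = 28 days to 70 + 14 − 28 = 56 days.
- End of radiation to the next scheduled chemistry: 6 weeks = 42 days; with the −4/+7 window, 38 to 49 days.
- Dose 4 to the next scheduled chemistry: 42 − 14 = 28 days. Dose 4 itself falls at 14 to 21 days (+7 window), so the range is 38 − 21 = 17 to 49 − 14 = 35 days.
- Day 28 chemistry to the next scheduled chemistry: 42 + 42 − 28 = 56 days to 70 + 42 − 28 = 84 days. The earliest case is one fraction given 14 days after Dose 3, with the + 6 weeks visit 4 days early: 14 + 0 + 38 = 52 days.

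Longer courses or unresolved radiation adverse events lengthen the gaps from Day 28. All these figures leave out any sample drawn because a site followed Section 4.2.2.1.

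**Radiation Therapy Period.** Scheduled samples: chemistry 0, CBC 1 (the Day 42-70 visit). A sample on the day of Dose 4 belongs to Post-Radiation Vaccination Period 1, since the Radiation Therapy Period ends the day before.

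**The case against.** The best defence is that the text already protects the patient. Section 4.2.2.1 is mandatory, and a blank cell does not repeal it. A site that reads both will draw the sample. Dose 4 is not given without assessment either: a medical assessment is due within 3 days before each dose, CBC is marked at Day 42-70 and at + 2 weeks, and laboratory tests are repeated when clinically indicated. All of this stands, and it limits the likely harm. It does not remove the conflict, because I found no statement of whether text or table governs.

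Three stronger readings are tempting, and the documents do not support them.

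- A reader might infer that liver tests are wrongly omitted as well. ALT, AST and bilirubin fall under the general rule, whose exception clause could reasonably cover a blank schedule cell. They are not in the stated minimum. The text is ambiguous, not contradictory.
- A reader might infer that the SAP's Radiation Therapy Period laboratory tables are in error because no chemistry is scheduled then. Summarizing by period is compatible with sparse or unscheduled samples. Whether a table separates no toxicity from not measured depends on shells that SAP Appendix 2 places in another document.
- A reader might infer that patients received Dose 4 without chemistry. The documents show what was scheduled, not what was drawn.

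**Conclusion.** The point holds. The schedule contradicts Section 4.2.2.1 on creatinine and electrolytes at one vaccination visit of the 14 after Day 0, and SAP Appendix 1 repeats the omission. This is an error in an operative table at the first post-radiation dose, so it should be corrected, but its reach is modest. The count rests on the schedule alone. The day counts from Day 28 also rest on the assumed end of radiation and are approximate. ORR, the stage 1 and stage 2 decision rules and the sample size are untouched. Showing the number of patients sampled in the Radiation Therapy Period tables would be a useful clarification, but its absence from the SAP text is not an error.

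**What to change.** 1. Mark Chemistry at End Radiation + 2 weeks in Protocol 1.5 and SAP Appendix 1, and state that the sample is drawn before dosing. The visit already draws CBC, TBNK and 6 × 10 + 8.5 = 68.5 mL of biomarker blood, so the cost is one more tube and no added visit. Dose 4 may have to wait for the result.
2. If Dose 4 visits are already over, report how many patients had creatinine and electrolytes before Dose 4. SAP Section 4 suggests that they are, since it discusses the first two post-radiation scans as past. The cost is one count from existing data.
3. Optional: in the by-period laboratory tables, show how many patients had at least one result in the period. Item 1 does not supply this for the Radiation Therapy Period, because a sample on the day of Dose 4 counts in the next period. The cost is one line per table, and the period definitions need not change.

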### 4.2.2.2 Evaluation of Response

Appropriate imaging with CT of the chest/abdomen/pelvis and MRI (if target lesion is best visualized by MRI) to reassess tumor extent and to determine tumor measurements will be performed 14 weeks after completion of radiotherapy and with each subsequent dose of vaccine thereafter (with windows for treatment as designated in the schedule of events, [Section 1.5](#)).

## 4.2.3 After Treatment Completion

Post-treatment follow-up will be conducted 30 (+/- 2) days after last dose of treatment. The visit should include a history and physical exam; labs with CBC/differential and serum chemistries; assessment of trial drug AEs; RECIST 1.1 assessment; and CT chest, abdomen, and pelvis, and MRI (if target lesion is best visualized by MRI). If patient had abnormal physical exam findings or abnormal lab values at the off-treatment time point, then the patient should have follow-up visit with the primary oncologist to focus on the abnormal finding(s). Results and report findings should be faxed or emailed to the trial team.

Once the 30 day follow up assessment is completed, the patient is then taken off trial.

Patients removed from trial for any reason must be followed for at least 30 days after the last dose of vaccine or until all toxicities have resolved to baseline or stabilized, whichever is later.

#### 4.2.4 Unscheduled Visits

Additional visits to the clinic may be necessary between scheduled visits based on a patient's health status and the investigator's clinical opinion. Unscheduled visits may be performed to repeat laboratory testing, ECG or physical exams due to a new development. Examinations performed at unscheduled visits will be documented in the source documents as well as in the respective Electronic Case Report Form (eCRF) sections for unscheduled visits.

#### 4.2.5 Withdrawal from Vaccination

Patients will be withdrawn from vaccination if any of the following is true:

- Target lesion disease progression as determined by
  - Radiographic disease progression by standard RECIST 1.1
  - Symptomatic disease progression by symptoms with concurrent evidence of any tumor enlargement
  - NOTE: A patient may continue on trial, at the investigator's discretion, with progression if he/she is eligible for local intervention for a non-target lesion progression
  - NOTE: A patient may remain on trial after initial evidence of target lesion disease progression until a confirmatory scan has been performed due to tumor swelling that can occur with radiotherapy and/or immunotherapy
- Patient withdrawal of consent (must document patient rationale for withdrawal)
- Positive pregnancy test
- Intercurrent illness or medical circumstances. If at any time the constraints of this protocol are detrimental to the patient's health, the patient may be removed from protocol therapy. In this event, the reasons for withdrawal will be documented.
- Adverse events meeting the following criteria: Evidence of any  $\geq$  Grade 3 allergic and  $\geq$  Grade 3 autoimmune reaction(s) attributed to vaccine (**except** Grade 3 endocrine-related immune toxicity or Grade 3 endocrine-related immune toxicity that resolves to Grade  $\leq$  1 clinically within 7 days of initiating supportive therapy); or if  $>$  Grade 2 toxicity attributed to vaccine persists for  $>$  28 days, the patient will not receive further vaccine injections. Patients who come off treatment must be followed on trial until resolution of toxicity and until disease progression.

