#### 4.2.6 Premature Discontinuation

Patients will discontinue the trial if any of the following are true:

- Participant requests to be withdrawn from trial; in this event, the reasons for withdrawal will be documented. If at all possible, the patient should return for the Post Treatment Follow-up Visit.
- A patient who is noncompliant with protocol guidelines may be removed from the trial at the discretion of the principal investigator.
- Disease progression, as described in Removal from Protocol Therapy [Section 4.2.5](#)
- Death.

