### 9.2 Prior and Concomitant Medication

All non-cancer treatment prior and concomitant medications taken in the 90 days prior to the screening visit will be captured. Prior cancer treatments will be captured indefinitely. In regards to SAE reporting: Any clinically relevant concomitant medication taken within 30 days prior to the onset of an SAE must be indicated as such within the SAE report. Any medications taken in response to the SAE are considered treatment medications, within the context of SAE reporting, and should also be indicated as such within the SAE report.

Anti-emetics and antidiarrheal agents may be administered as required, but are not anticipated to be needed and should not be used prophylactically. Selection of the specific antiemetic regimen is at the discretion of the treating physician. Antiemetic regimens should not include dexamethasone or other steroids.

Toxicities thought to be autoimmune related and attributable to vaccine would lead to discontinuation of vaccine and symptomatic treatment. This may also include the use of immune suppressive treatments such as glucocorticoids and replacement hormones if indicated.

Other supportive care with blood components, antibiotics, analgesics, general medical therapy, etc., will be delivered as required. Any patients taking antibiotics for any reason must complete that course of therapy and be free of evidence of further infection before receiving any dose of vaccine.

Live, attenuated vaccine including influenza vaccine (FluMist), are not allowed within 4 weeks of Day 1 and throughout the trial.

Symptomatic anemia should be treated with appropriate red blood cell or erythropoietin support.

Other investigational therapies will not be allowed while a patient participates in this trial.

No additional therapies, besides those dictated by the trial (vaccine and radiotherapy), to treat chordoma are allowed on trial. In the case of progression of a non-target lesion, local therapeutic interventions are allowed on protocol, including surgery or radiation. In these cases, the primary target lesion is still the only target to be used for assessment of efficacy. Interventions to other sites are allowed to provide treatment alternatives for patients while they remain on trial to evaluate the results of the experimental treatment.

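### Protocol 4.2.3 ends follow-up 30 days after the last vaccine dose, short of the 12-month response window, and 4.2.5 gives its target-lesion criterion an all-lesion label

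*Protocol*

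**What the plan says.** **Stopping vaccine (Protocol 4.2.5).** The progression criterion opens with "Target lesion disease progression as determined by" and has two parts. One is "Radiographic disease progression by standard RECIST 1.1"; the other is "Symptomatic disease progression by symptoms with concurrent evidence of any tumor enlargement". The first note under it lets a patient continue, at the investigator's discretion, "with progression if he/she is eligible for local intervention for a non-target lesion progression".

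**Leaving the trial.** Protocol 4.2.6 ends participation for "Disease progression, as described in Removal from Protocol Therapy", which refers back to 4.2.5. Protocol 4.2.3 sets a visit 30 days after the last dose and states: "Once the 30 day follow up assessment is completed, the patient is then taken off trial". The last sentence of the adverse-event bullet in 4.2.5 says something different: "Patients who come off treatment must be followed on trial until resolution of toxicity and until disease progression".

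**What the endpoint needs.** Protocol 10.2 and 10.5 define the primary endpoint on irradiated target lesions by modified RECIST 1.1, within 12 months after radiation, and 10.5 states that non-target progression is not progression under those criteria. Protocol 9.2 allows local treatment of non-target lesions and adds: "In these cases, the primary target lesion is still the only target to be used for assessment of efficacy". SAP 3.6 says responses are followed until everyone has reached 12 months after radiation or has progressed.

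**How an early exit is counted.** Under SAP 3.4.2, a patient with no recorded CR or PR who leaves early is a non-responder, and is counted as progressed in the by-time-point PFS. SAP 3.5.3.2 provides for replacement after non-target progression only before the patient is evaluable.

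**The concern.** The wording and the follow-up rule both work against the endpoint.

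First, the protocol attaches the term standard RECIST 1.1 to assessment of all lesions (10.2, 10.4.5.3, 10.5) and uses modified RECIST 1.1 for target lesions. A site that turns to Appendix 1 finds a new lesion coded as progression. It also finds non-target progression coded as progression, with a footnote limiting that to exceptional circumstances. The symptomatic criterion does not name the target lesion. The first note would hardly be needed if non-target progression could never stop treatment.

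Second, and with more consequence, 4.2.3 ends observation by reference to the last vaccine dose, whereas the endpoint runs from the end of radiation. Any patient who stops vaccine early without target progression (for toxicity, medical circumstances or non-target progression) can leave well before 12 months. The protocol itself expects responses to accrue with time: 10.4.3 says the response rate may rise with further follow-up. Responses that would have appeared on later scans are then lost and scored as failures, in a design whose power is barely above 80%.

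**Working it through.** **1. The plan's own figures.** Inputs from Protocol 10.3: 10 patients, stop at 0 responders; 19 more, reject the null at 4 or more of 29; null rate 5%, alternative 20%.

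Rejection probability = sum over x = 1 to 10 of P(X1 = x) × P(X2 ≥ 4 − x), with X1 ~ Bin(10, p) and X2 ~ Bin(19, p).

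At p = 0.20: 0.2684 × 0.7631 + 0.3020 × 0.9171 + 0.2013 × 0.9856 + 0.1209 = 0.8011. The last term is P(X1 ≥ 4).

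At p = 0.05 the rejection probability is 0.0468, the early-stopping probability is 0.95^10 = 0.599, and the expected size is 10 + 19 × (1 − 0.599) = 17.6. All agree with the protocol.

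**2. Scans inside the window.** Protocol 1.5 schedules scans at weeks 14, 26, 38 and 50 after radiation; the next is at week 62. Section 4.2.2.2 ties scans after week 14 to vaccine doses, so a patient who has stopped vaccine has no further scheduled scan except at the 30-day visit.

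- Exit after week 14 keeps 1 of 4 scheduled scans; exit after week 26 keeps 2 of 4.
- The 30-day scan falls at week 14 + 30/7 = 18.3 if the week-14 dose was given, or at week 10 + 30/7 = 14.3 if the last dose was at week 10.
- A 30-day scan at about week 18 can confirm a response seen at week 14. A response first seen on the 30-day scan cannot be confirmed on trial, because 10.5 requires a repeat scan at least 4 weeks later.

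**3. Such a patient stays in the analysis.** Protocol 10.4.1 needs the two primes, the pre-radiation boost, completed radiation, 3 of 4 boosters in the 14 weeks after radiation, and one post-baseline scan. A patient who meets these and leaves after week 14 is evaluable, is not replaced, and without a CR or PR counts as a non-responder.

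**4. Illustration of size.** The documents do not say how many patients would be affected, so 1 to 3 is an assumption. Let k stage 2 patients respond with probability r × p instead of p, so that X2 = Bin(19 − k, p) + Bin(k, r × p). Spreading the response chance evenly over the four scans (also an assumption) gives r = 0.25 for exit after week 14 and r = 0.5 for exit after week 26.

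For k = 1, r = 0.25, p = 0.20: 0.2684 × 0.7373 + 0.3020 × 0.9050 + 0.2013 × 0.9829 + 0.1209 = 0.7900.

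| Affected in stage 2 | Power, r = 0.25 | Power, r = 0.5 |
|---|---|---|
| 0 | 80.1% | 80.1% |
| 1 | 79.0% | 79.4% |
| 2 | 77.8% | 78.6% |
| 3 | 76.4% | 77.7% |

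Type I error at p = 0.05 only falls: with three affected it is 3.75% (r = 0.25) or 4.06% (r = 0.5), against 4.68%.

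**The case against.** **The target-only reading of 4.2.5 is the better one.** Both sub-criteria sit under a heading limited to the target lesion, the second note repeats that limit, and 4.2.6 only imports it. Footnote 10 to the schedule, Protocol 10.5 and the SAP definition of progressive disease point the same way. The word standard could also mean ordinary rather than immune-related thresholds, and 10.5 assigns the all-lesion evaluation to external reviewers, not to sites. This stands: a reader might infer that the protocol requires removal for non-target progression, and the documents do not support that. They only fail to rule it out.

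**The wording change alone helps few patients.** Local treatment is allowed on trial (9.2), and SAP 3.5.3.2 deliberately takes off patients whose non-target progression needs systemic treatment. What remains is patients who can have neither local nor systemic treatment and are not stopped for medical circumstances. This also stands, and it is why the follow-up rule matters more than the label.

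**Early stoppers may already be covered.** The heading of 4.2.3 speaks of treatment completion, and 4.2.5 asks for follow-up until progression. But that sentence sits inside the adverse-event bullet and sets no imaging schedule, and the off-trial sentence in 4.2.3 makes no exception. The conflict remains.

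**Larger losses should not be read into this.** If affected patients could not respond at all, one to three would give 78.6–75.0% power in stage 2 and 76.7–67.9% in stage 1. Neither range measures the defect. These patients have a week-14 scan, so their response chance is not zero. The stage 1 decision needs only two post-baseline scans (Protocol 10.4.3, SAP 3.6), which week 14 and the 30-day visit can supply, and SAP section 4 shows that stage 2 was already under way.

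**Conclusion.** The concern holds as an inconsistency with a modest, conservative effect. Protocol 4.2.3 conflicts with the 12-month endpoint window, with SAP 3.6 and with the last sentence of 4.2.5. Separately, 4.2.5 uses the all-lesion label for a criterion that 10.5 and the SAP assess on irradiated target lesions.

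The consequence is that an evaluable patient can be scored a non-responder after as little as a quarter of the scheduled scans. This can lower the observed response rate and power. It does not inflate type I error, and it leaves every stated design figure intact. A response already recorded is kept.

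The loss is about one percentage point of power for one stage 2 patient, and about two to four points for three. This rests on an assumed count and an assumed even spread of response over the scans; neither is in the documents. The label in 4.2.5 is a minor wording matter. The follow-up conflict is the part that can change a patient's outcome in the primary analysis.

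**What to change.** 1. **Protocol 4.2.5, wording.** Replace the standard RECIST 1.1 criterion with *modified RECIST 1.1 (irradiated target lesions only, per Section 10.5)*. In the symptomatic criterion, require enlargement of an irradiated target lesion. State that non-target progression or a new lesion is not by itself a progression criterion for withdrawal. The medical-circumstances bullet and the systemic-treatment exit in SAP 3.5.3.2 stay as they are. Section 4.2.6 follows automatically because it refers to 4.2.5.

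2. **Protocol 4.2.3, follow-up.** Add an exception: *a patient who stops vaccine without target-lesion progression, has not withdrawn consent and has not started systemic therapy continues the scheduled target-lesion imaging through week 50 after radiation or target-lesion progression, whichever is first, plus any confirmatory scan required by Section 10.5.* Change the last sentence of 4.2.5 to match, so that only one follow-up rule remains.

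The non-responder rule in SAP 3.4.2 and the SAP limit on replacement need no change.

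**Cost.** Item 1 is text only. Item 2 is a small design addition: for each such patient, up to three scans already on the schedule, plus a confirmatory scan if a response is seen. It needs no extra patients or readers and leaves the decision rule alone. It helps only patients still inside their 12-month window when it takes effect.
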